3. LIST OF ACRONYMS/ABBREVIATIONS

Acronym/Abbreviation	Description
AE	Adverse event
AESI	Adverse event of special interest
ATC	Anatomical therapeutic class
AUC	Area under the curve
BLOQ	Below the limit of quantification
BMI	Body mass index
BV	Blood volume
CRF	Case report form
CSR	Clinical study report
CV	Coefficient of variation
D1 Preop	Day 1 pre-operation
ECG	Electrocardiogram
EMA	European Medicines Agency
FDA	Food and Drug Administration
GMR	Geometric Mean Ratio
Hct	hematocrit
Hb	hemoglobin
ICF	Informed consent form
ICH	International Conference on Harmonization
IV	Intravenous
MedDRA	Medical dictionary for regulatory affairs
n	Number of subjects
NRS	Numeric Rating Scale
PACU	Post-anesthesia care unit
PK	Pharmacokinetics
PT	Preferred Term
SAE	Serious adverse event
SAP	Statistical analysis plan
SD	Standard deviation
SE	Standard error
SOC	System Organ Class
SWAS	Surgical Wound Aspect Score
TEAE	Treatment-emergent adverse event
TKA	Total knee arthroplasty
TLF	Tables, listings and figures
TUG	Timed Up-and-Go
TXA	Tranexamic Acid
WHO-DD	World Health Organization - Drug Dictionary Enhanced

4. INTRODUCTION

This Statistical Analysis Plan (SAP) describes the planned statistical analysis and reporting of the clinical study 404-C-201 titled “A Randomized, Single-Blind, Active-Controlled, Dose-Ranging Study to Evaluate the Pharmacokinetics, Safety, and Efficacy of Local Administration of DepoTXA for Reduced Postsurgical Bleeding in Subjects Undergoing Total Knee Arthroplasty”. The primary objective of this study is to evaluate pharmacokinetics of DepoTXA compared to intravenous (IV) tranexamic acid (TXA).

The structure and content of this SAP provides sufficient detail to meet the requirements identified by the US Food and Drug Administration (FDA), European Medicines Agency (EMA), and International Conference on Harmonisation (ICH) of Technical Requirements for Registration of Pharmaceuticals for Human Use: Guidance on Statistical Principles in Clinical Trials (US Federal Register, 1998). All work planned and reported for this SAP will follow internationally accepted guidelines, published by the American Statistical Association (American Statistical Association, 1999) and the Royal Statistical Society (Royal Statistical Society, 1993), for statistical practice.

The purposes of this SAP are to:

- Outline the types of analyses and presentations of data that will form the basis for drawing conclusions regarding the study objectives and hypotheses outlined in the protocol.
- Explain in detail how the data will be handled and analyzed, adhering to commonly accepted standards and practices for Good Statistical Practice.

The planned analyses identified in this SAP may be included in clinical study reports (CSRs), regulatory submissions, or manuscripts. Post-hoc exploratory analyses not necessarily identified in this SAP may be performed to further examine study data. Any post-hoc, unplanned, or exploratory analyses performed will be clearly identified as such in the final CSR.

The following documents were reviewed in preparation of this SAP:

- Amendment 2 of Protocol 404-C-201 issued on 27SEP2017.
- CRF issued on 01MAR2017.
- ICH Guidance on Statistical Principles for Clinical Trials (E9).

The reader of this SAP is encouraged to also read the clinical protocol and other identified documents for details on the planned conduct of this study. Operational aspects related to collection and timing of planned clinical assessments are not repeated in this SAP unless relevant to the planned analyses.

5. STUDY OBJECTIVES

5.1. Primary Objective

The primary objective of this study is to evaluate the pharmacokinetics of DepoTXA compared to IV TXA.

5.2. Secondary Objectives

The secondary objectives of this study are to evaluate (1) the safety of DepoTXA, (2) the efficacy of DepoTXA (over 5 days) compared to IV TXA, and (3) a potential dose-related response to DepoTXA at 400, 800, and 1200 mg (33 mg/mL).

6. STUDY OVERVIEW

This is a Phase 2, randomized, single-blind, active-controlled dose-ranging study in patients scheduled to undergo total knee arthroplasty (TKA). Approximately 60 subjects (15 per treatment group) are planned for enrollment. Subjects will be randomized in a 1:1:1:1 ratio to receive DepoTXA 400 mg, DepoTXA 800 mg, DepoTXA 1200 mg, or IV TXA (Cyklokapron® 1 gram).

Blood samples for PK analysis will be obtained at baseline (prior to study drug administration); at 5, 15, and 30 minutes; and at 1, 2, 4, 6, 8, 12, 16, and 24 hours after study drug administration for all treatment groups. Additional blood samples will be collected at 36, 48, 60, 72, and 96 hours after study drug administration for DepoTXA-treated subjects.

Postsurgical efficacy assessments will include measurement of blood loss (as assessed by hemoglobin [Hb] and hematocrit [Hct] levels), transfusion requirement, knee flexion, timed up-and-go (TUG) test, knee and thigh measurements, numeric rating scale (NRS_ pain scores), days to independent ambulation, and the surgical wound aspect score (SWAS).

Postsurgical safety assessments will include vital signs, neurological assessment, clinical laboratory testing (hematology, chemistry, and coagulation), 12-lead electrocardiogram (ECG), and adverse event (AE) monitoring. Subject monitoring will include, but not be limited to, changes in vision, neurologic function, or renal function; and occurrence of hematoma, wound dehiscence/disruption, surgical site infection (per Centers for Disease Control and Prevention definition), nausea, vomiting, and diarrhea.

Adverse events of special interest (AESI) include changes in color vision, venous thromboembolism or pulmonary embolism, and oliguria. If an AESI or serious AE (SAE) occurs during the study, an unscheduled PK blood sample must be collected. In addition, vital signs, the neurological assessment, and clinical laboratory tests must be conducted, as appropriate. If a subject experiences changes in color vision, an ophthalmological consultation must be ordered.

7. DEFINITIONS

Study Day

Study Day 1 is defined as the day of surgery. Study day is calculated as the date of event minus the date of surgery plus one (1), if the date of event is on or after the date of surgery. Study day is based on the calendar dates, thus days before the date of study drug administration have negative values while those on or after the date of surgery have positive values.

Treatment-emergent Adverse Events

A TEAE will be any adverse event or pre-existing medical condition that worsens in intensity after the start of study drug and within 30 days of the last dose.

Time 0 (zero)

Time 0 is defined as the date and time of the start of study drug administration.

Time Periods

All schedule times have a window associated with them (see Time and Events Schedule in the Protocol for individual timepoint windows). Various time frames that are dependent on these windows are used in the data analyses. Table 1 defines the actual elapsed times with allowance for the windows that can be included in the window.

Table 1: Time Periods

Defined time frame	Acceptable elapsed times
5 min	3-7 min
15 min	12-18 min
30 min	25-35 min
1h	50-70 min
2h	105-135 min
4h	225-255 min
6h	345-375 min
8h	450-510 min
12h	690-750 min
16h	15-17h
24h	23-25h
36h	34-38h
48h	46-50h
60h	57-63h
72h	68-76h
96h	90-102h
120h	114-126h
Study Day 7	Study Day 6-8
Study Day 14	Study Day 13-15
Study Day 30 Call	Study Day 27-33
Study Day 60 Call	Study Day 57-63

If there are two or more data points that fit the time window the data point that occurs the closest, in absolute value, to the scheduled observation will be used.

Baseline

Baseline is defined as the last available measurement or assessment prior to the start of study drug administration.

8. ANALYSIS SETS

The safety analysis set will include all subjects who received study drug. Subjects in the safety analysis set will be assessed according to the actual treatment they received.

The efficacy analysis set will include all subjects who received study drug and underwent the planned surgery. Subjects in the efficacy analysis set will be assessed according to their randomized treatment, regardless of the actual treatment they received.

The PK analysis set will include all subjects who received study drug, provided sufficient samples to allow for calculation of PK parameters ($AUC_{[0-t_{last}]}$ and global, C_{max} and T_{max}) required for analysis, and who do not have significant protocol deviations that may invalidate or bias the results. Subjects in the PK analysis set will be assessed according to the actual treatment they received.

9. STATISTICAL METHODS OF ANALYSIS

9.1. General Principles

The statistical analyses will be reported using summary tables, listings, and figures (TLFs). All analyses and tabulations will be performed using SAS® Version 9.1 or later. Continuous variables will be summarized using descriptive statistics and categorical variables will be tabulated with the number and percentage of subjects. Unless otherwise noted, percentages will be based on the number of subjects in the treatment group within the population.

Individual subject data will be provided in listings. All listings will be sorted by treatment, site, subject, and, if applicable, collection date and time.

Unless otherwise stated summaries will present data across all sites (overall).

Unless otherwise noted, tabulations of categorical data will present only those categories appearing in the data.

On all figures presenting multiple treatments,

- IV TXA will be represented in black with solid lines and dots;
SAS Code: symbol interpol=spline width=1 value=dot line=1 c=black;
- DepoTXA 400 will be represented in red with solid lines and hollow triangles;
SAS Code: symbol interpol=spline width=1 value=triangle line=1 c=red;
- DepoTXA 800 will be represented in green with solid lines and hollow circles;
SAS Code: symbol interpol=spline width=1 value=circle line=1 c=green;
- DepoTXA 1200 will be represented in purple with solid lines and hollow squares;
SAS Code: symbol interpol=spline width=1 value=square line=1 c=purple.

Figures presenting a single subject will be represented in black with solid lines and dots.

All tables will present DepoTXA 400 mg, DepoTXA 800 mg, DepoTXA 1200 mg, and IV TXA as separate columns, in this order.

9.1.1. Handling Missing Values

9.1.1.1. Post-baseline Cummulative Blood Loss

It is expected that all necessary information to calculate post-baseline cumulative blood loss will be complete. Any such information that is missing and cannot be obtained through query resolution may be imputed, on a case-by-case basis. There will be no hypothesis testing and it is assumed that missing data on cumulative blood loss will be rare or non-existent, thus a single imputation method is expected to provide useful enough information to plan for the next phase of DepoTXA development. The following single imputation procedures will be used:

- a) A simple linear imputation will be used for a missing value from the closest observed values prior and post for non-monotone missing data.
- b) If the missing data are monotone, then last observed carried forward will be used.

It is currently assumed that approximately 84% of the total cumulative blood loss will occur within 12 hours post-surgery and approximately 94% of the total cumulative blood loss will occur within 24 hours post-surgery (Kumar, 2005).

9.1.1.2. Adverse Event Date or Time

It is expected that all necessary information on adverse events and the surgeries (start and stop date and time) will be complete. Unless an adverse event can be excluded as a treatment emergent by the known start and stop date/time, the adverse event should be considered treatment emergent.

9.1.1.3. Concomitant Medications Date or Time

It is expected that all necessary information on medications and surgeries (start and stop date and time) will be complete. Unless a medication can be excluded as a concomitant by the known start and stop date/time, the medication should be considered concomitant.

9.1.1.4. Adverse Event Severity or Relationship to Study Drug

If severity of an AE is not reported, then for tables of AEs by severity, the missing severity will not be imputed, but will be described in the footnote for the table. If relationship to study drug is not reported for an AE, then for tables of study-drug related AEs, the event will be assigned the relationship of 'definite'. Tables presenting related AEs will include all AEs with relationships of 'possible', 'probable' or 'definite' as assessed by the investigator or defined as 'definite' when no investigator assessment is made.

9.1.2. Multiplicity Adjustments

Not applicable.

9.2. Subject Disposition

Subject disposition summaries will include the number of subjects that were:

- Screened,
 - Screen failure
 - Reasons for screen failure (Did not meet Inclusion #1, ect.)
- Randomized
 - Randomized not treated
 - Randomized treated
 - Randomized did not undergo surgery
 - Randomized underwent surgery
- In the safety analysis set
- In the efficacy analysis set
- In the PK analysis set
- Completed the study as planned
- Discontinued from the study
- By reason for discontinuation from the study.

Percentages will be reported for the screen failures and enrolled subjects using the number of subjects screened as the denominator and for the safety, efficacy and PK analysis sets, completed study, discontinued from study, and reasons for discontinuation with the number of subjects

randomized as denominator. The percentages for the safety analysis set will use the number of subjects randomized and treated as the denominator.

Safety and PK analysis sets data will be presented as treated. All other data will be presented as randomized.

The disposition summary will present the data for each treatment group and across treatment groups (Total). This summary table will present overall sites and for each site separately.

9.3. Description of Demographics and Baseline Characteristics

9.3.1. Demographics

The summary of demographic data will present:

- Age (years) – descriptive statistics
- Sex – n (%)
- Ethnicity – n (%)
- Race – n (%)
- ASA classification – n (%)
- Country – n (%)

Age is calculated from the date the subject signed the informed consent form (ICF) and birth date. It is presented as the number of years between, rounding down to the nearest integer year. The following macro will be used to derive age:

```
%macro age_integer (dob=,eventdate=);
  floor((intck('month',&dob.,&eventdate.) - (day(&eventdate.)<day(&dob.)))/12);
%mend age_integer;
```

For partial birthdates, impute the first of the month for missing day and January for missing month to calculate age. It is presumed that birth year is known.

The demographic summary will present the data for each treatment group. Summaries will be provided for all (safety, efficacy, and PK) analysis sets. This summary will present overall sites and for each site separately.

9.3.2. Baseline Characteristics

The summary of baseline characteristic data will present:

- Total Blood Volume (BV; in mL)
- Height (cm)
- Weight (kg)
- Body Mass Index (BMI) (kg/m²)

The formula for BMI is $w/(h^2)$, where w is weight in kilograms and h is height in meters. Weight in pounds will be converted to kilograms using the conversion factor of 2.2046 pounds to 1 kilogram. Height in inches will be converted to centimeters using the conversion factor of 2.54 centimeters to 1 inch. Height in centimeters will be converted to meters using the conversion factor of 100 centimeters to 1 meter.

Baseline characteristics summaries will present the data for each treatment group and across treatment groups (Total). Summaries will be provided for all (safety, efficacy and PK) analysis sets. This summary table will show summaries across all sites and for each site separately.

Descriptive statistics (n, mean, standard deviation [SD], median, minimum and maximum) will be provided for total blood volume, height, weight, and BMI.

9.4. Surgery Characteristics

The following surgery characteristics will be summarized: duration of surgery, length of incision, tourniquet use, duration of tourniquet use, maximum pressure of tourniquet, and type of anesthesia.

9.5. Medical and Surgical History

Medical and surgical history recorded at the screening visit will be coded using Medical Dictionary for Regulatory Activities (MedDRA) version 19.1 or higher. Medical and surgical history will be listed by treatment and subject as well as summarized by system organ class (SOC) and preferred term (PT).

9.6. Prior and Concomitant Medications

Prior and concomitant medications will be coded using the World Health Organization Drug Dictionary Enhanced (WHO-DD) September 2016 and will be classified according to the default anatomical therapeutic chemical (ATC) classification system term and PT.

Prior medications are defined as medications with a stop date and time prior to the start of study drug administration.

Concomitant medications are defined as medications taken after the start of study drug administration (i.e., started prior to the start of study drug administration and continued after or started within 30 days after the start of study drug administration).

Prior and concomitant medications will be summarized separately using n (%) of subjects for each treatment group and across treatment groups by ATC class term and PT for the safety analysis set. Subjects may have more than one medication per ATC category and PT. At each level of subject summarization, a subject will be counted once if one or more medications are reported by the subject at that level.

A listing mapping the ATC term and PT to verbatim term will be presented.

9.7. Measurements of Treatment Compliance

Study treatment is administered by a party other than the subject, therefore compliance is ensured.

9.8. Efficacy Analysis

No formal statistical hypothesis testing will be performed. The following endpoints will be summarized using descriptive statistics:

- Total blood loss as measured by Hb and Hct levels upon arrival at the post-anesthesia care unit (PACU) and at 6, 12, 24, 48, 72, 120 hours, and Day 7
- Incidence of transfusion (number of units/subject, number of subjects transfused)

- Time to 90° passive and active knee flexion at 24, 48, and 72 hours for patients enrolled prior to Amendment 2 and by AM/PM at 24, 48, and 72 hours for patients enrolled on Amendment 2
- Time to complete TUG test once on study day 1 (postsurgical day 0), twice a day on study day 2 (6:00 - 10:00 and 18:00 - 22:00), at hospital discharge, and on study day 7
- Change in knee and thigh measurements on the morning of postsurgical day 2 and at the day 7 follow-up visit
- NRS Pain Scores upon arrival at the PACU, at each in-hospital vital sign assessment beginning with the 48-hour assessment, and at the Day 7 follow-up visit
- Days to Independent Ambulation assessed beginning at Day 7 follow-up visit
- Surgical Wound Aspect Score (SWAS) on the morning of postsurgical day 2 and on day 7

9.8.1. Total Blood Loss

Total loss will be calculated separately using two separate methods. The first method is based on Hct and the second method is based upon Hb. Total blood loss will be calculated at 6, 12, 24, 48, 72, 120 hours, and Day 7 postsurgery for each subject. Descriptive statistics summarizing the total blood loss will be summarized by postsurgical timepoint and treatment group for the efficacy analysis population for each method. Baseline is considered the last value measured before the surgery.

Total BV in mL will be calculated using the Nadler formula ([Nadler 1962](#)) at baseline by

$$BV_{baseline} = (a * h^3 + b * w + c)$$

where h = height (m), w = baseline weight (kg), $\{a=0.3669, b=0.03219, c=0.6041\}$ for males and $\{a=0.3561, b=0.03308, c=0.1833\}$ for females. The $BV_{baseline}$ is used in methods 1 and 2 to determine blood loss.

Method 1 ([Gibon 2013](#)):

Total RBC loss is in mL calculated by the following formula:

$$RBC_{lost} = BV_{baseline} * (Hct_{baseline} - Hct_{postop\ hour}) + BV_{transfused}$$

where $Hct_{baseline}$ is measured as the volume percentage of red blood cells in the blood at baseline, $Hct_{post-op\ hour}$ is measured as the volume percentage of red blood cells in the blood at the specified postsurgical timepoint in hours, total $BV_{baseline}$ is measured in mL, and $BV_{transfused}$ is the mL volume of blood transfused to the subject.

Method 2 ([Gao et al, 2015](#)):

Another method of calculating blood loss is presented by Gao as follows:

$$Hb_{loss} [g] = BV_{baseline} [\text{mL}] \cdot (Hb_{baseline} [\text{g/L}] - Hb_{postop} [\text{g/L}]) \cdot 0.001 [\text{L/mL}] + Hb_t [\text{g}],$$

$$Hb_t = BV_{transfused} [\text{Unit}] \cdot 52 [\text{g/Unit}], \text{ and}$$

$$RBC_{lost} [\text{mL}] = 1000 \times Hb_{loss} [\text{g}] / Hb_{baseline} [\text{g/L}],$$

where Hb_{loss} is the total loss of hemoglobin in gram, $BV_{baseline}$ is the presurgery blood volume in mL, $Hb_{baseline}$ and Hb_{postop} are the presurgery and post surgery hemoglobin concentration in g/L, Hb_t is the amount of hemoglobin transfused in gram, $BV_{transfused}$ is the banked blood transfused in Unit, and RBC_{lost} is the total volume of RBC lost. The above formulae can be simplified as

$$RBC_{lost} = \frac{BV_{baseline} * (Hb_{baseline} - Hb_{postop}) + BV_{transfused} * 52000}{Hb_{baseline}}.$$

Total blood loss upon arrival at the PACU and at 6, 12, 24, 48, 72, 120 hours, and Day 7 will be summarized using descriptive statistics [n, mean, SD, minimum, median, and maximum] for method 1 and method 2 separately. When both methods are presented together on the same graph, method 1 will be represented using a solid line (line=1) and method 2 will be represented using a dashed line (line 2).

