program_name

Pacira Pharmaceuticals
Listing 16.2-4.2: Tourniquet Characteristics - Randomized Subjects
Treatment: TTTTTT

(Page X of Y)

Protocol: 404-C-201

Site	Subject	Date	Tourniquet Used?	Tourniquet Time			Maximum Pressure (mmHg)
				Start	Stop	Duration (hr)	
XXX	XXX-YYYY	DDMONYYYY	xxx	HH:MM	HH:MM	XX.X	xxx
XXX	XXX-YYYY	DDMONYYYY	xxx	HH:MM	HH:MM	XX.X	xxx
XXX	XXX-YYYY	DDMONYYYY	xxx	HH:MM	HH:MM	XX.X	xxx
XXX	XXX-YYYY	DDMONYYYY	xxx	HH:MM	HH:MM	XX.X	xxx
XXX	XXX-YYYY	DDMONYYYY	xxx	HH:MM	HH:MM	XX.X	xxx
XXX	XXX-YYYY	DDMONYYYY	xxx	HH:MM	HH:MM	XX.X	xxx

Source: list SAS datasets used to create listing
SAS X.Y

DDMONYYYYTHH:MM
program_name

Pacira Pharmaceuticals (Page X of Y)
Listing 16.2-5: Study Drug Administration - Randomized Subjects

Protocol: 404-C-201

Site	Subject	Study Treatment			Date	Start Time	Stop Time	Total Volume (mL)
		Randomized	Actual					
XXX	XXX-YYYY	XXXXXXXXXXXXXX	XXXXXXXXXXXXXX		DDMONYYYY	HH:MM	HH:MM	X
XXX	XXX-YYYY	XXXXXXXXXXXXXX	XXXXXXXXXXXXXX		DDMONYYYY	HH:MM	HH:MM	X
XXX	XXX-YYYY	XXXXXXXXXXXXXX	XXXXXXXXXXXXXX		DDMONYYYY	HH:MM	HH:MM	X
XXX	XXX-YYYY	XXXXXXXXXXXXXX	XXXXXXXXXXXXXX		DDMONYYYY	HH:MM	HH:MM	X
XXX	XXX-YYYY	XXXXXXXXXXXXXX	XXXXXXXXXXXXXX		DDMONYYYY	HH:MM	HH:MM	X
XXX	XXX-YYYY	XXXXXXXXXXXXXX	XXXXXXXXXXXXXX		DDMONYYYY	HH:MM	HH:MM	X

Source: list SAS datasets used to create listing
SAS X.Y

DDMONYYYYTHH:MM
program_name

Pacira Pharmaceuticals
Listing 16.2-6.1.1: Calculated Blood Loss - Method 1 - Randomized Subjects
Randomized Treatment: TTTTTT

(Page X of Y)

Protocol: 404-C-201

Site	Subject	Date and Time	Timepoint	Blood Volume Transfused (mL)	Hematocrit (%)	Calculated Blood Volume (mL)	Calculated Blood Loss (mL)
XXX	XXX-YYYY	DDMONYYYYTHH:MM	Baseline	xxx.x	xxx.x	xxxx.x	N/A
		DDMONYYYYTHH:MM	PACU	xxx.x	xxx.x	xxxx.x	xxx.x
		DDMONYYYYTHH:MM	6 hrs	xxx.x	xxx.x	xxxx.x	xxx.x
		DDMONYYYYTHH:MM	12 hrs	xxx.x	xxx.x	xxxx.x	xxx.x
		DDMONYYYYTHH:MM	24 hrs	xxx.x	xxx.x	xxxx.x	xxx.x
		DDMONYYYYTHH:MM	48 hrs	xxx.x	xxx.x	xxxx.x	xxx.x
		DDMONYYYYTHH:MM	72 hrs	xxx.x	xxx.x	xxxx.x	xxx.x
		DDMONYYYYTHH:MM	120 hrs	xxx.x	xxx.x	xxxx.x	xxx.x
		DDMONYYYYTHH:MM	Day 7	xxx.x	xxx.x	xxxx.x	xxx.x
		DDMONYYYYTHH:MM	Baseline	xxx.x	xxx.x	xxxx.x	N/A
XXX	XXX-YYYY	DDMONYYYYTHH:MM	PACU	xxx.x	xxx.x	xxxx.x	xxx.x
		DDMONYYYYTHH:MM	6 hrs	xxx.x	xxx.x	xxxx.x	xxx.x
		DDMONYYYYTHH:MM	12 hrs	xxx.x	xxx.x	xxxx.x	xxx.x
		DDMONYYYYTHH:MM	24 hrs	xxx.x	xxx.x	xxxx.x	xxx.x
		DDMONYYYYTHH:MM	48 hrs	xxx.x	xxx.x	xxxx.x	xxx.x
		DDMONYYYYTHH:MM	72 hrs	xxx.x	xxx.x	xxxx.x	xxx.x

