		DDMONYYYYTHH:MM	120 hrs	xxx.x	xxx.x	xxxx.x	xxx.x
		DDMONYYYYTHH:MM	Day 7	xxx.x	xxx.x	xxxx.x	xxx.x

Note: Blood volume transfused is since the last Timepoint. Blood Volume is calculated according to section 9.8.1 of the Statistical Analysis Plan for study 404-C-201: For method 1, blood loss is in mL calculated by: $RBC_{lost} = BV_{baseline} * (Hct_{baseline} - Hct_{post-op\ hour}) + BV_{transfused}$

Source: list SAS datasets used to create listing
SAS X.Y

DDMONYYYYTHH:MM
program_name

Note to programmer: Sort by collection date and time. Timepoints outside of the schedule windows should be listed under "Scheduled Timepoint" as "Unscheduled". Do not split a subject's data across pages.

Pacira Pharmaceuticals
Listing 16.2-6.1.2: Calculated Blood Loss - Method 2 - Randomized Subjects
Randomized Treatment: TTTTTT

(Page X of Y)

Protocol: 404-C-201

Site	Subject	Date and Time	Timepoint	Blood Volume Transfused (g)	Hemoglobin (g/dL)	Calculated Blood Volume (mL)	Calculated Blood Loss (mL)
XXX	XXX-YYYY	DDMONYYYYTHH:MM	Baseline	xxx.x	xxx.x	xxxx.x	N/A
		DDMONYYYYTHH:MM	PACU	xxx.x	xxx.x	xxxx.x	xxx.x
		DDMONYYYYTHH:MM	6 hrs	xxx.x	xxx.x	xxxx.x	xxx.x
		DDMONYYYYTHH:MM	12 hrs	xxx.x	xxx.x	xxxx.x	xxx.x
		DDMONYYYYTHH:MM	24 hrs	xxx.x	xxx.x	xxxx.x	xxx.x
		DDMONYYYYTHH:MM	48 hrs	xxx.x	xxx.x	xxxx.x	xxx.x
		DDMONYYYYTHH:MM	72 hrs	xxx.x	xxx.x	xxxx.x	xxx.x
		DDMONYYYYTHH:MM	120 hrs	xxx.x	xxx.x	xxxx.x	xxx.x
		DDMONYYYYTHH:MM	Day 7	xxx.x	xxx.x	xxxx.x	xxx.x
		DDMONYYYYTHH:MM	Baseline	xxx.x	xxx.x	xxxx.x	N/A
XXX	XXX-YYYY	DDMONYYYYTHH:MM	PACU	xxx.x	xxx.x	xxxx.x	xxx.x
		DDMONYYYYTHH:MM	6 hrs	xxx.x	xxx.x	xxxx.x	xxx.x
		DDMONYYYYTHH:MM	12 hrs	xxx.x	xxx.x	xxxx.x	xxx.x
		DDMONYYYYTHH:MM	24 hrs	xxx.x	xxx.x	xxxx.x	xxx.x
		DDMONYYYYTHH:MM	48 hrs	xxx.x	xxx.x	xxxx.x	xxx.x
		DDMONYYYYTHH:MM	72 hrs	xxx.x	xxx.x	xxxx.x	xxx.x
		DDMONYYYYTHH:MM	120 hrs	xxx.x	xxx.x	xxxx.x	xxx.x
		DDMONYYYYTHH:MM	Day 7	xxx.x	xxx.x	xxxx.x	xxx.x

Blood volume transfused is since the last Timepoint. Blood Volume is calculated according to section 9.8.1 of the Statistical Analysis Plan for study 404-C-201: For method 2, blood loss is in mL calculated by:

$$RBC_{lost} = \frac{1000 * (BV_{baseline} * (Hb_{baseline} - Hb_{post-op\ hour})) * 0.001 + 52 * BV_{transfused}}{Hb_{baseline}}$$

Source: list SAS datasets used to create listing
SAS X.Y

DDMONYYYYTHH:MM
program_name

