Exclusion 17 Malignancy in the last 2 years, with the exception of non-metastatic basal cell or squamous cell carcinoma of the skin or localized carcinoma in situ of the cervix.

Exclusion 18 Suspected or known history of drug or alcohol abuse within the previous year.

Exclusion 19 Body weight <50 kg (110 pounds) or a body mass index >44 kg/m².

Exclusion 20 Administration of an investigational drug within 30 days or 5 elimination half-lives of such investigational drug, whichever is longer, prior to study drug administration, or planned administration of another investigational product or procedure during the patient's participation in this study.

Source: list SAS datasets used to create listing
SAS X.Y

DDMONYYYYTHH:MM
program_name

Pacira Pharmaceuticals Listing 16.2-16: Pregnancy Test - All Subjects					(Page X of Y)	Protocol: 404-C-201		
Treatment: TTTTTTTTTT								
Site	Subject	Visit	Date	Sex	Childbearing Potential	Pregnancy Test	Result	
XXX	XXX-YYYY	Screening	DDMONYYYY	Female	YES		NEGATIVE	
		D1 Preop	DDMONYYYY					
	XXX-YYYY	Screening	DDMONYYYY	Female	NO		NOT APPLICABLE	
		D1 Preop	DDMONYYYY					
	XXX-YYYY	Screening	DDMONYYYY	Male			NOT APPLICABLE	
		D1 Preop	DDMONYYYY					

Source: list SAS datasets used to create listing
SAS X.Y

DDMONYYYYTHH:MM
program_name

Note to programmer: Possible results for screening tests are: POSITIVE, NEGATIVE, NOT DONE, or NOT APPLICABLE (if Childbearing Potential = 'NO' or Sex = 'Male').

Pacira Pharmaceuticals Listing 16.2-17: Protocol Deviations - All Subjects Treatment: TTTTTT				(Page X of Y)	Protocol: 404-C-201
Site	Subject	Start Date and Time	Protocol Deviation Coded Term	Description	Action Taken
XXX	XXX-YYYY	DDMONYYYYTHH:MM	XXXXXXXXXXXXXXXXXXXX	XXXXXXXXXXXXXXXXXXXX	XXXXXXXXXXXXXXXXXXXX

Source: list SAS datasets used to create listing
SAS X.Y

DDMONYYYYTHH:MM
program_name

Pacira Pharmaceuticals
Listing 16.2-18.1: Pharmacokinetic Concentrations - All Subjects
Treatment: DepoTXA 400 (Enrolled After Protocol Amendment 2)

Protocol: 404-C-201

Site	Subject	Date and Time of Dose				Time From Dose			
		Infusion Date	Start Time	End Time	PK Sample	Scheduled (hr)	Actual (hr)	Deviation (mins)	Concentration (ng/mL)
XXX	XXX-YYYY	DDMONYYYY	HH:MM	HH:MM	DDMONYYYYTHH:MM	0	XX	X	BLOQ
					DDMONYYYYTHH:MM	0.08	0.XX	X	XXX.X
					DDMONYYYYTHH:MM	0.25	0.XX	X	XXX.X
					DDMONYYYYTHH:MM	0.50	X	X	XXX.X
					DDMONYYYYTHH:MM	1	ND		
					DDMONYYYYTHH:MM	2	X	-X	XXX.X
					DDMONYYYYTHH:MM	4	X	X	XXX.X
					DDMONYYYYTHH:MM	6	X	X	XXX.X

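### Blood-loss formulas as printed are wrong: section 9.8.1 labels litres as mL and leaves haematocrit as a percentage, and the Method 2 listing counts a transfused unit as 52 instead of 52000

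*SAP*

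**What the plan says.** **Blood volume.** SAP section 9.8.1 says "Total BV in mL will be calculated using the Nadler formula". It prints BV_baseline = a × h³ + b × w + c, with h in metres, w in kilograms, "a=0.3669, b=0.03219, c=0.6041" for men, and a = 0.3561, b = 0.03308, c = 0.1833 for women. It then treats BV_baseline as mL in both methods. Listings 16.2-6.1.1 and 16.2-6.1.2 also head this quantity in mL.

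**Method 1.** The loss is BV_baseline × (Hct_baseline − Hct_postop) + BV_transfused in mL. Haematocrit is defined as a volume percentage, and the listing column is in %.

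**Method 2.** Section 9.8.1 multiplies the whole haemoglobin loss, transfused haemoglobin included, by 1000 and divides by Hb_baseline in g/L. Its simplified form carries the term "BV_{transfused} * 52000". Here Hb_t "is the amount of hemoglobin transfused in gram" and BV_transfused "is the banked blood transfused in Unit".

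**Method 2 listing.** In the footnote of Listing 16.2-6.1.2 the bracket after the factor 1000 encloses only the haemoglobin-fall product. The numerator then continues with "0.001 + 52 * BV_{transfused". The columns show transfused volume in g and haemoglobin in g/dL.

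**Transfusion period.** Both listing footnotes describe the transfused volume as the amount given after the preceding timepoint. Section 9.8.1 does not say whether the term is cumulative. Section 9.1.1.1 calls the endpoint cumulative blood loss after baseline.

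**The concern.** A programmer who follows 9.8.1 literally mixes scales. The fall terms use blood volume in litres, while the transfusion terms are in mL. This is more than a uniform rescaling that a change of label would repair: an untransfused subject shows almost no loss, and a transfused subject shows little except the transfusion. It would affect every blood-loss table, listing and figure for both methods, and the plot of 24-hour AUC against blood loss.

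The listing formula is a separate conflict. For the same transfused subject it does not give the 9.8.1 value. Section 9.1.1.1 expects these data to help plan the next phase of development, so the derivation should be correct as written even though nothing is tested.

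**Working it through.** **Inputs.** The coefficients, the definitions and the factors 52 and 52000 come from section 9.8.1. Body-size limits come from Exclusion 19 in Listing 16.2-15.2 ("Body weight <50 kg (110 pounds) or a body mass index >44 kg/m²"). Heights, the individual weights, haemoglobin and haematocrit values are assumed for illustration. The factors of 1000 and 100 do not depend on them.

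**1. Blood volume as printed**
- Man, 1.75 m, 85 kg: 0.3669 × 1.75³ + 0.03219 × 85 + 0.6041 = 5.307
- Woman, 1.62 m, 75 kg: 0.3561 × 1.62³ + 0.03308 × 75 + 0.1833 = 4.178
- Small eligible woman, 1.50 m, 50 kg: 3.039
- Large eligible man, 1.95 m, BMI 44 (44 × 1.95² = 167.3 kg): 8.710

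These are litres. The stated mL is not reproduced; the shortfall is a factor of 1000.

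**2. Method 2, BV 5.307, Hb 133 to 100 g/L**
- No transfusion, as printed: 5.307 × 33 / 133 = 1.32
- No transfusion, BV in mL: 5307 × 33 / 133 = 1317 mL
- One unit, as printed: 1.32 + 52000 / 133 = 1.32 + 390.98 = 392.3
- One unit, BV in mL: 1317 + 391 = 1708 mL

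**3. Method 1, haematocrit fall of 10 percentage points, no transfusion**

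| Blood volume | Haematocrit | Result |
|---|---|---|
| litres (as printed) | fraction | 5.307 × 0.10 = 0.53 |
| litres (as printed) | percentage (as printed) | 5.307 × 10 = 53 |
| mL | percentage (as printed) | 5307 × 10 = 53,070 |
| mL | fraction | 5307 × 0.10 = 531 mL |

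Only the last row is consistent. As printed, the two scale faults partly offset each other, so correcting blood volume alone leaves Method 1 wrong by a factor of 100.

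**4. Method 2 listing formula**

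The numerator is 1000 × (BV × fall) × 0.001 + 52 × BV_transfused. The 1000 and the 0.001 cancel on the first term and never reach the second. With units and g/L, one unit adds:
- By 9.8.1: 52000 / 133 = 391 mL (433 at Hb 120, 347 at Hb 150)
- By the listing: 52 / 133 = 0.39 mL

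The column headings admit other inputs. At Hb 133 g/L (13.3 g/dL), one unit then adds:
- Units and g/dL: 52 / 13.3 = 3.9 mL
- Grams of haemoglobin (52 per unit) and g/L: 52 × 52 / 133 = 20 mL
- Grams of haemoglobin and g/dL: 52 × 52 / 13.3 = 203 mL
- Grams of blood (assumed 300 g) and g/dL: 52 × 300 / 13.3 = 1173 mL

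None of these gives 391 mL, and they miss it in both directions. With no transfusion, the listing and 9.8.1 agree.

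**The case against.** **The intent is clear.** The mL unit is repeated throughout, and a blood volume near 5.3 in a column masked for four digits would be noticed. That lowers the chance of an unnoticed error in the listings. It does not correct the specification, and the baseline-characteristics table has a mask that would accept 5.3.

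**The listing footnote may be only a note.** The SAP does not say that listings are computed separately from tables, and the full Method 2 derivation in 9.8.1 handles the transfusion term correctly. So a reader might infer that listings and tables will disagree, but the SAP shows only that the two printed formulas do. The bracket deserves a check against the typeset page, though as it stands the brackets balance and the expression has one algebraic reading.

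**Direction.** A reader might infer that the listing always understates the transfusion term. It does with units and g/L, but the grams-of-blood reading above overstates it, so no general direction can be claimed.

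**Interval transfusion.** A reader might also infer that earlier transfusions drop out of later losses. With BV 5000 mL, Hb 133 falling to 100 g/L at both 24 and 48 hours, and two units given between 12 and 24 hours, loss would appear to go from (5000 × 33 + 104000) / 133 = 2023 mL at 24 hours to 5000 × 33 / 133 = 1241 mL at 48 hours. The SAP does not establish this. The footnote may describe only the displayed column, 9.8.1 sets no interval limit, and 9.1.1.1 points to a cumulative quantity. This part needs clarifying; it is not a shown error.

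**Conclusion.** Two printed statements are definitely wrong: the mL label on a formula that returns litres, and the Method 2 listing term of 52 per unit where 9.8.1 has 52000. Each is a factor of 1000, the second when units and g/L are used. The haematocrit scale in Method 1 is a related fault of a factor of 100 and must be settled together with the blood-volume correction. The listing's headings in g and g/dL do not match the units and g/L of 9.8.1.

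The blood-volume and haematocrit faults reach every subject. The listing formula and the transfusion-period wording matter only for transfused subjects, and the SAP gives no transfusion rate. Blood loss is a secondary endpoint, summarised descriptively without hypothesis tests. It might be inferred that the comparison between arms is biased; nothing in the SAP shows that. The point should be fixed before programming, with weight limited accordingly.

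**What to change.** 1. In 9.8.1 write BV_baseline (mL) = 1000 × (a × h³ + b × w + c).
2. In Method 1, in 9.8.1 and in Listing 16.2-6.1.1, state that haematocrit enters as a fraction, or divide the percentage difference by 100.
3. In Listing 16.2-6.1.2 print the 9.8.1 form: [BV_baseline (mL) × (Hb_baseline − Hb_postop) + 52000 × BV_transfused (units)] / Hb_baseline, with Hb in g/L. Head the transfusion column in units and Hb in g/L, or state the conversion. If the column shows grams of transfused haemoglobin, that value takes the factor 1000, so that 52 is not applied twice.
4. State in 9.8.1 and in both footnotes that BV_transfused is cumulative from baseline to the draw, and that the volume shown since the preceding timepoint is for display only.

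The cost is a few lines in 9.8.1, two footnotes, some column headings and the matching code. No new data are needed: Listing 16.2-6.2 already holds transfusion start and end times and the number of units.
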